7. RESEARCH PROCEDURES

General Procedures. Subjects who meet the inclusion criteria will reside on the Clinical Research Unit (CRU) at the University of Kentucky Medical Center while they participate. During their participation in the research protocol, subjects will not be allowed to leave the CRU unattended, nor will visitors be allowed. After completing the protocol, all subjects will be debriefed and offered a referral to a drug use treatment program. Subjects will be enrolled for approximately one month. Experimental sessions and dosing will be conducted as shown in Table 1. After three days of maintenance on each zolmitriptan dose (i.e., double the time necessary to achieve steady state concentrations as outlined below; Dixon et al., 1997), the reinforcing and subjective effects of intravenous cocaine (0, 10, and 30 mg/70 kg), as well as a range of impulsive behaviors, will be measured across three experimental sessions. Note, the maximum intravenous cocaine dose will be 40 mg regardless of weight, but we will continue to refer to this dose condition at 30 mg/70 kg throughout the protocol. Following completion of the Practice Session, a nurse from the UKHealthCare Vascular Access Team (VAT) will insert a needle into the subject's arm. The needle will be removed and a long intravenous midline catheter (approximately 3 – 5 inches) will stay in the vein near the subject's armpit. The placement of this midline catheter will allow for longer-term intravenous access (e.g., 30 days) to receive fluids (i.e., saline) and cocaine than a typical venous catheter that would be placed prior to experimental sessions. This eliminates the need to re-insert short-term catheters for IV access (e.g., 2 – 3 days). The removal of the midline catheter will occur upon completion of the last experimental session or when deemed necessary by the study physicians and/or hospital policy. Peripheral intravenous catheter may be inserted in the subject's arm if the midline catheter needs to be removed or if an unforeseen event obstructs administration of cocaine (e.g., leaking).

Table 1.

Day	Details
0	Admission to the CRU. Practice Session wherein subjects will be familiarized with the experimental session tasks.
1	Medical Safety Session. Subjects will receive the cocaine doses to be tested in this study (0, 10 and 30 mg/70 kg) separated by 60 minutes.
2-7	Placebo maintenance. Placebo administered twice daily (0700 and 1900 hours).

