Self-Administration Task. After sampling the intravenous cocaine dose (0, 10, and 30 mg/70 kg), subjects will complete 5 choice trials between that dose and \$6.00, separated by 60 minutes. The money amount was selected based on previous research because it functions as a reinforcer but does not completely suppress drug-taking behavior ([name] et al., 2020). The initial response requirement for either choice (i.e., cocaine or money) will be 400 mouse clicks. Response requirements will increase by 200 responses for previously chosen options. For example, if a subject chooses cocaine at the first opportunity, the next response requirement for cocaine would be 600 responses, but the response requirement for money would remain at 400 responses. If a subject were to choose one option exclusively, the response requirements would be 400, 600, 800, 1000 and 1200 responses. These response requirements were based on our previous human laboratory studies that have tested various ratio parameters to maximize drug-maintained responding while minimizing placebo self-administration ([name] et al., 2016; 2020; Sevak et al., 2010; [name] et al., 2010). Subjects may choose not to complete a ratio for either reinforcer during a choice trial (i.e., an omission), but physiological measures and the assessment battery will still be completed as scheduled and the ratio requirements for each reinforcer will carry forward to the next trial. Break points for cocaine and money will be the primary outcome variables.

Assessment Battery. A battery of subjective and cognitive tasks will also be used to assess drug effects to meet Aims 2 and 3. Standard safety and tolerability measures will also be included.

Subjective Outcomes (Appendix A). Two valid and widely used questionnaires that measure various aspects of mood and drug effects will be included: 1) Drug-Effect Questionnaire ([name] et al., 2003) and 2) Adjective Rating Scale (Oliveto et al., 1992). The Cocaine Craving Questionnaire (Dudish-Poulsen and Hatsukami, 1997) will also be included. These measures will be completed prior to each cocaine sampling dose and at 15-minute intervals after administration of the sampling dose.

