Data Analysis. All data will be analyzed statistically as outlined below using SPSS. Only data from completing subjects will be included in the analyses. Any subjects who do not complete the study will be replaced until we accrue 20 completers. Statistical significance refers to $p \leq 0.05$.

Aim 1: Demonstrate that 5-HT_{1b} activation reduces the reinforcing effects of cocaine. The reinforcing effects of cocaine will be determined by evaluation of break points for cocaine and money from the concurrent progressive-ratio choice task. For cocaine and money break points, each of which have one data point for each dose condition, data will be analyzed using two-factor repeated-measures ANOVA. Cocaine (0, 10, and 30 mg/70 kg) and zolmitriptan (0, 2.5, 5, and 10 mg/day) will be factors for these analyses. A significant augmentation (i.e., leftward shift in the dose-response curve) or attenuation (i.e., rightward shift in the dose-response curve) of the effects of cocaine will be inferred if the main effect of the zolmitriptan or the cocaine-zolmitriptan interaction attains statistical significance in the ANOVA. If the cocaine-zolmitriptan interaction attains statistical significance, the Mean Square Error (MSE) term will be used to conduct Tukey's HSD *post-hoc* test to make appropriate pair-wise comparisons between means.

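### Aim 1 infers a rightward or leftward shift of the cocaine curve from omnibus F tests that do not examine curve shape, and plans no follow-up after a main effect alone

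*Combined protocol and SAP*

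**What the plan says.** All of this is in the combined protocol and SAP.

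- **Outcome.** Break points for cocaine and money are primary (section 7, Self-Administration Task; section 17, Data Monitoring Plan).
- **Model.** Section 7, Data Analysis, Aim 1: "each of which have one data point for each dose condition, data will be analyzed using two-factor repeated-measures ANOVA". The levels are: "Cocaine (0, 10, and 30 mg/70 kg) and zolmitriptan (0, 2.5, 5, and 10 mg/day) will be factors for these analyses". That is a 0 mg condition and two active cocaine doses, crossed with four zolmitriptan conditions.
- **Decision rule.** The sentence begins "A significant augmentation (i.e., leftward shift in the dose-response curve) or attenuation (i.e., rightward shift in the dose-response curve" and ends by saying that this "will be inferred if the main effect of the zolmitriptan or the cocaine-zolmitriptan interaction attains statistical significance in the ANOVA". On the attenuation side it therefore runs: "attenuation (i.e., rightward shift in the dose-response curve) of the effects of cocaine will be inferred if the main effect of the zolmitriptan", or its interaction with cocaine, is significant.
- **Follow-up.** "If the cocaine-zolmitriptan interaction attains statistical significance, the Mean Square Error (MSE) term will be used to conduct Tukey's HSD" comparisons. Nothing is specified for a significant main effect without a significant interaction.
- **Elsewhere.** The Aim 2, Aim 3 and physiological data paragraphs use the same either/or rule without the shift parentheses.

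The plan fits no dose-response curve, estimates no ED50 or potency ratio, and specifies no contrast that addresses shape.

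**The concern.** A rightward shift is a statement about potency: the same response needs more cocaine. A lower maximum is a different statement. A fall that also appears when the infusion is saline may not be about cocaine at all; it could reflect less willingness to work for any infusion. The rule gives all three one label.

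The main-effect route is the weakest. The main effect averages over 0, 10 and 30 mg/70 kg, whereas a purely horizontal shift leaves the 0 mg cell where it was. An equal fall at every cocaine dose would satisfy the rule, be called a rightward shift, and meet no planned comparison that could correct the label.

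The rule also has no sign, and it applies to both break points. For money, attenuation of cocaine's effect should appear as an increase, and the text does not say so. What is at stake is the wording of the primary conclusion, not the validity of the F tests.

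**Working it through.** **1. The plan's own figure.** Section 7, Power Analysis, gives 80% power at 20 completers, alpha 0.05, f = 0.27. For a within-subject effect, λ = f²·n·m/(1−ρ). With m = 4 zolmitriptan levels and ρ = 0.5 (assumed; not stated), λ = 0.0729 × 20 × 4 / 0.5 = 11.66 on 3 and 57 df, and power is 0.7995. The figure reproduces under that reading. It is power for an omnibus effect and says nothing about a shift.

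**2. What each pattern does to the cells** (no numbers needed).

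| True change on zolmitriptan | 0 mg | Active doses | Main effect | Interaction |
|---|---|---|---|---|
| Rightward shift | unchanged | lower | yes | yes |
| Lower maximum | unchanged | lower | yes | yes |
| Equal fall everywhere | lower | lower | yes | no |

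All three can trigger the rule. An exact upward mirror image of the first gives the same F power, because the tests carry no sign.

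**3. How often the rule fires.** Assumed, not from the documents: mean = E0 + Emax·d/(ED50 + d), normal errors, cell SD 300 clicks (range 200 to 400), ρ = 0.5, n = 20. Baseline E0 = 100, Emax = 1000, ED50 = 10 gives means of 100/600/850. Scenarios at 2.5, 5 and 10 mg/day:

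- Rightward: ED50 15, 20, 30. At 10 mg/day: 100/350/600.
- Lower maximum: Emax 850, 750, 650. At 10 mg/day: 100/425/587.5.
- Equal fall of 60, 100, 150 clicks at every cocaine dose, from 250/675/887.5, ignoring the floor.

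Main-effect λ = 3n·Σ(zolmitriptan mean − grand mean)² / [SD²(1−ρ)]. For the rightward case the zolmitriptan means are 516.7, 455.6, 411.1 and 350.0, the sum of squares is 14,877, and λ = 60 × 14,877 / 45,000 = 19.8, so power is 0.964. For the equal fall the sum of squares is 12,075 and λ = 60 × 12,075 / 45,000 = 16.1, so power is 0.918; its interaction λ is zero. Simulation of the either/or rule (20,000 trials per scenario):

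| Scenario | Main effect | Interaction | Either, SD 300 (SD 400 to 200) | Main effect only, SD 300 |
|---|---|---|---|---|
| Rightward | 0.97 | 0.61 | 0.99 (0.86–1.00) | 0.37 |
| Lower maximum | 0.90 | 0.54 | 0.96 (0.77–1.00) | 0.42 |
| Equal fall | 0.92 | 0.05 | 0.93 (0.69–1.00) | 0.87 |

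**4. Can two active doses separate rightward from downward?** ED50 doubled gives 100/433/700; Emax × 0.75 gives 100/475/662.5. The differences are −41.7 and +37.5 clicks, about one fifth of the 200-click step. The variance of a paired change is 2 × 45,000 / 20 = 4,500. The best two-dose contrast has noncentrality √[(41.7² + 37.5²)/4,500] = 0.84, hence power 0.13 (0.10 to 0.24 for SD 400 to 200).

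**5. A second model.** Five binomial choices per session, ED50 12 mg, maximum 0.9, between-subject SD 1.0 and session SD 0.6 on the logit scale, 0 mg choice probability 0.02 to 0.10 (all assumed). The rule fires in about 57–65% of trials when the maximum falls to 0.60 at 10 mg/day, 71–76% when ED50 rises to 32 mg, and 85–89% for an equal logit fall that includes 0 mg. Mean changes at 10 and 30 mg/70 kg are about −135 and −190 (lower maximum) against −189 and −177 (rightward). The gaps of 54 and 13 clicks are below one standard error of about 85.

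**The case against.** The strongest reply is that Aim 1 asks only whether zolmitriptan attenuates cocaine reinforcement. The operative word is attenuation, the parentheses merely gloss it, and the sign can be read from the cell means. That stands as far as it goes, and it is why the remedy is small. But the gloss is written as an identity, for the primary outcome, in the sentence that fixes what will be concluded.

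A reader might infer something stronger: that the design can never tell a rightward from a downward shift, so every significant result carries an unsupportable claim. The documents do not support that.

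- **Separability depends on the assumed curve.** In the second model the two scenarios nearly coincide at the top dose by choice of parameters: 0.9 × 30/62 = 0.435 against 0.6 × 30/42 = 0.429. With ED50 moving from 6 to 16 mg, Hill slope 2 and 0 mg probability 0.05, the changes are about −352 and −152 (rightward) against −191 and −272 (downward). The 10-minus-30 contrasts are −200 and +81, a gap of about 280 with a standard error of about 105. With Hill slope 1 and ED50 4 to 6 mg the gap is again only about one standard error. A fall at 10 mg/70 kg with no change at 30 mg/70 kg would favour a rightward shift.
- **A non-significant interaction does not show equal displacement.** Under the true rightward shift in step 3, the main effect is significant without the interaction in 37% of trials. That outcome leaves the label untested; it does not refute it.
- **The two shifts are not opposite messages.** Both mean less cocaine reinforcement at the doses tested.

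The equal-fall example is also constrained by the task: the ratios were chosen "to maximize drug-maintained responding while minimizing placebo self-administration", so a 0 mg break point near the floor has little room to fall. This limits how large a uniform fall can be, but it does not make the main effect a test of shape.

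**Conclusion.** The point holds as a defect in the inference rule and its wording. The Aim 1 rule attaches a claim about curve shape to two omnibus tests that do not examine it, and after a main effect alone nothing planned would check the claim. That part follows from the text and needs no simulation.

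The size is conditional. In the settings tried, the rule fired at broadly similar rates for rightward, downward and non-specific changes, and the main-effect-only route was common. Separating rightward from downward with two active doses was weak under many plausible assumptions, though not impossible. Each simulated figure belongs to one assumption set. The shift wording is confined to Aim 1. The finding does not question the F tests themselves or the aim of showing attenuation. It merits a change because the outcome is primary and the edit is cheap.

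**What to change.** In section 7, Data Analysis, Aim 1:

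1. Delete both parentheses that equate augmentation and attenuation with a shift. This matches the Aim 2, Aim 3 and physiological data paragraphs.
2. Extend the planned Tukey comparisons to follow a significant zolmitriptan main effect as well as a significant interaction.
3. Infer attenuation only when a comparison of a zolmitriptan dose with 0 mg/day, at 10 and/or 30 mg/70 kg cocaine, shows a lower cocaine break point or a higher money break point. Define augmentation as the reverse.
4. Report the 0 mg cocaine comparison alongside, to show whether the change is specific to cocaine.
5. State that the ANOVA does not distinguish rightward from downward shifts and that neither will be claimed from it.

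**Cost.** No change to data collection, doses or sample size. The sponsor gives up a mechanistic label and accepts a stricter criterion. How much stricter depends on the SD and on the Tukey family, which the plan does not define. If all 12 cell means form the family (5% studentized range 4.72 with 114 df), the smallest significant difference at SD 300 is 4.72 × √(45,000/20) = 224 clicks; for SD 200 to 400 it runs from 149 to 298. The assumed rightward fall at 10 mg/day in step 3 is 600 − 350 = 250 clicks, so the cost is small at SD 200 and real at SD 400. The family should be named and the power of these comparisons checked, since the stated 80% applies to an omnibus effect.

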Aim 1: Demonstrate that 5-HT_{1b} activation reduces the reinforcing effects of cocaine. The primary hypotheses, related to our first specific aim, are that: 1) cocaine will function as a reinforcer on the concurrent progressive-ratio choice task that was developed and validated in our laboratory ([name] et al., 2016; 2020) and 2) zolmitriptan will attenuate the reinforcing effects of cocaine, leading to the reallocation of behavior towards the non-drug alternative (i.e., \$6.00) available on the choice task.

Aim 2: Demonstrate that 5-HT_{1b} activation attenuates subjective abuse-related effects of cocaine (e.g., positive subjective effects, craving). The primary hypotheses related to our second specific aim are that: 1) cocaine will produce prototypic effects on subjective outcomes (e.g., increased ratings of drug liking) and 2) zolmitriptan will attenuate these effects (e.g., reduce cocaine related increases on ratings of drug liking).

Aim 3: Demonstrate that 5-HT_{1b} activation attenuates impulsive responding that is a common characteristic of cocaine use disorder and is mediated by the 5-HT system. The primary hypothesis related to our third specific aim is that zolmitriptan will attenuate impulsive responding (e.g., reduce delay discounting of drug and money). This hypothesis is based upon our previous findings and the preclinical outcomes described above.

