Aim 2: Demonstrate that 5-HT_{1b} activation attenuates subjective abuse-related effects of cocaine (e.g., positive subjective effects, craving). Three sets of analyses will be conducted on the subjective effect data. First, data will be analyzed as peak effect (i.e., maximum effect observed following administration of cocaine sampling doses) using two-factor repeated-measures ANOVA. Cocaine (0, 10, and 30 mg/70 kg) and zolmitriptan (0, 2.5, 5, and 10 mg/day) will be factors for these analyses. A significant augmentation or attenuation of the effects of cocaine will be inferred if the main effect of the zolmitriptan or the cocaine-zolmitriptan interaction attains statistical significance in the ANOVA. If the cocaine-zolmitriptan interaction attains statistical significance, the MSE term will be used to conduct Tukey's HSD *post-hoc* test to make appropriate pair-wise comparisons between means. Second, Area Under the Curve (AUC) will be calculated for each subject using the trapezoidal method and analyzed in the same fashion as peak-effect data. Third, these data will be analyzed by repeated-measure ANOVA with cocaine, zolmitriptan and time as factors. The MSE term for the cocaine-zolmitriptan-time interaction will then be used to conduct Tukey's *post-hoc* tests to make appropriate pair-wise comparisons.

Aim 3: Demonstrate that 5-HT_{1b} activation attenuates impulsive responding that is a common characteristic of cocaine use disorder and is mediated by the 5-HT system. For the impulsivity outcomes, each of which have only one data point for each dose condition, data will be analyzed using two-factor repeated-measures ANOVA. Cocaine (0, 10, and 30 mg/70 kg) and zolmitriptan (0, 2.5, 5, and 10 mg/day) will be factors for these analyses. A significant augmentation or attenuation of the effects of cocaine will be inferred if the main effect of the zolmitriptan or the cocaine-zolmitriptan interaction attains statistical significance in the ANOVA. If the cocaine-zolmitriptan interaction attains statistical significance, the MSE term will be used to conduct Tukey's HSD *post-hoc* test to make appropriate pair-wise comparisons between means.

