Physiological data. Three sets of analyses will be conducted on the cardiovascular outcomes and body temperature data. First, data will be analyzed as peak effect using two-factor repeated-measures ANOVA. Cocaine (0, 10, and 30 mg/70 kg) and zolmitriptan (0, 2.5, 5, and 10 mg/day) will be factors for these analyses. A significant augmentation or attenuation of the effects of cocaine will be inferred if the main effect of the zolmitriptan or the cocaine-zolmitriptan interaction attains statistical significance in the ANOVA. If the cocaine-zolmitriptan interaction attains statistical significance, the MSE term will be used to conduct Tukey's HSD *post-hoc* test to make appropriate pair-wise comparisons between means. Second, AUC will be calculated for each subject using the trapezoidal method and analyzed in the same fashion as peak-effect data. Third, these data will be analyzed by repeated-measure ANOVA with cocaine, zolmitriptan and time as factors. The MSE term for the cocaine-zolmitriptan-time interaction will then be used to make appropriate pair-wise comparisons.

Safety and tolerability data. For items from the UKU, which will have one data point per day, data will be analyzed using a two-factor repeated-measures ANOVA. Zolmitriptan (0, 2.5, 5, and 10 mg/day) and day will be factors for these analyses. The MSE term for the zolmitriptan-day interaction will then be used to make appropriate pair-wise comparisons.

Evaluating Relevant Biological Variables. We will conduct exploratory analyses to evaluate potential effects of relevant biological variables. Specifically, we will repeat the analyses described above including factors like sex, age, race, and other drug use to determine whether and how these variables might influence study outcomes. Although exploratory, these outcomes can inform future grant applications in terms of how individual differences influence responses to 5-HT_{1b} activation in people with cocaine use disorder.

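### Break points and impulsivity: a zolmitriptan main effect alone counts as a change in cocaine's effects, but no dose is compared with placebo unless the interaction is significant

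*Combined protocol and SAP*

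**What the plan says.** Section 7, Data Analysis, specifies a two-factor repeated-measures ANOVA (three cocaine doses by four zolmitriptan doses) for Aims 1 and 3. Two rules follow, and the same pair applies to both aims.

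- Declaration: augmentation or attenuation of cocaine's effects "will be inferred if the main effect of the zolmitriptan or the cocaine-zolmitriptan interaction attains statistical significance in the ANOVA".
- Follow-up: "If the cocaine-zolmitriptan interaction attains statistical significance, the Mean Square Error (MSE) term will be used to conduct Tukey's HSD".

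The Aim 1 text also glosses augmentation as a leftward and attenuation as a rightward shift of the cocaine dose-response curve.

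These outcomes have a single value per cell: "For cocaine and money break points, each of which have one data point for each dose condition", and "For the impulsivity outcomes, each of which have only one data point for each dose condition". So they have no time-course analysis. The subjective data do have one, and its pairwise tests do not depend on a significant interaction: "The MSE term for the cocaine-zolmitriptan-time interaction will then be used to conduct Tukey's". The physiological data are handled likewise: "The MSE term for the cocaine-zolmitriptan-time interaction will then be used to make appropriate pair-wise comparisons".

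The hypotheses in Section 1 are directional: "zolmitriptan will attenuate the reinforcing effects of cocaine, leading to the reallocation of behavior towards the non-drug alternative", and "The primary hypothesis related to our third specific aim is that zolmitriptan will attenuate impulsive responding". Section 17 names the break points as primary and adds only repeated-measures ANOVA at 5%.

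**The concern.** There are two routes to a positive finding, and only one leads to pairwise tests. On the main-effect route the conclusion rests on an F test with 3 numerator degrees of freedom. That test has no sign and singles out no dose. The primary outcome could be declared affected with no zolmitriptan dose tested against placebo, although the drug-dose text in Section 7 treats the testing of several doses as central to the study's value.

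Two features sharpen this.

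- The main effect averages over the 0 mg cocaine condition. A general shift in responding would satisfy the rule without any shift of the cocaine dose-response curve.
- The Aim 3 hypothesis is not tied to cocaine dose, so the pattern it most naturally predicts is a main effect, which is the pattern left without follow-up.

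Direction is also a live question. Section 1 reports that selective agonists of this class enhanced cocaine's reinforcing effects during ongoing administration, although zolmitriptan itself attenuated them.

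**Working it through.** **Inputs from the documents.** 20 completers; 3 cocaine by 4 zolmitriptan levels, all within subject; alpha 0.05; f = 0.27 at 80% power and f = 0.54 as the progressive-ratio example, observed with another drug (Section 7, Power Analysis). **Assumed, because the documents give none:** correlation ρ = 0.5, normality, compound symmetry, and either equal SDs or SDs of 4:15:22 across the cocaine doses.

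**1. The plan's own figure.** For a four-level within-subject factor, λ = f²·n·m/(1−ρ) = 0.27² × 20 × 4 / 0.5 = 11.66. On 3 and 57 df this gives 79.95% power, so the stated 80% reproduces. A 12-cell reading with ρ = 0 also fits (79.7%), so the documents do not settle which was used.

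**2. Scale.** Let the effect rise in equal steps over zolmitriptan dose to D SDs at the top dose. The steps 0, 1/3, 2/3, 1 have squared deviations summing to 0.5556, so f = D·√(0.5556/4) = 0.373·D. Then D = 0.72 is f = 0.27 and D = 1.45 is f = 0.54.

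**3. Main-effect-only results, effect at both active cocaine doses and none at 0 mg.** With equal SDs and D = 0.72:

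- Main effect: λ = 60 × (0.72 × 2/3)² × 0.5556 / 0.5 = 15.36, power about 0.90.
- Interaction: λ = 20 × 0.72² × 0.5556 × (6/9) / 0.5 = 7.68, power about 0.49.
- Main effect without interaction: 0.90 × (1 − 0.49) = 0.46.

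Simulation (20,000 runs per row) agrees and extends this:

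| Scenario | Equal SDs | SDs 4:15:22 |
|---|---|---|
| D = 0.6 | 50% | 38% |
| D = 0.72 (f = 0.27) | 46% | 25% |
| D = 0.72, ρ = 0.3 | 50% | 37% |
| D = 0.72, ρ = 0.7 | 25% | 5% |
| D = 0.72 at 30 mg only | 16% | 6% |
| D = 1.0 | 18% | 2% |
| D = 1.45 (f = 0.54) | under 1% | 0% |

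**4. Effect equal at all cocaine doses, equal SDs.** The interaction is null, so main-effect-only probability is main-effect power × 0.95. For D = 0.5, λ = 60 × 0.5² × 0.5556 / 0.5 = 16.67, power about 0.93, product 0.88. For D = 0.72 and 1.45, power is about 1 and the product is 0.95. The share does not fade as the effect grows.

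**5. No true effect.** Two tests at 5% give 1 − 0.95² = 9.75% if independent. Simulation gives 9.4% with equal SDs and 10.9% with SDs 4:15:22.

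**6. What a follow-up would add at D = 0.72.** Apply Tukey to the four zolmitriptan marginal means after a main-effect-only result, and to the four means within each cocaine dose after an interaction. Trials with a significant planned active-versus-placebo comparison rise from 49% to 93% (equal SDs) and from 73% to 97% (4:15:22). With the effect at 30 mg only, the rises are 47% to 60% and 78% to 82%.

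**7. Direction.** For the monotone patterns with D of 0.6 or more, the top-dose mean fell on the wrong side of placebo in 0.0% of main-effect-only runs (about 0.2% with the effect at 30 mg only). A mixed pattern is different. With the low dose up, the top dose down and main-effect power set to 80%, marginal Tukey tests in main-effect-only trials found a dose below placebo in 23%, a dose above in 24%, and no difference from placebo in 55%. A trial can fall in both of the first two groups.

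**The case against.** The best reply is that the gap is narrow. Direction can be read from the means, and for monotone effects that reading is almost never wrong. The Aim 1 text does define direction through left and right shifts. Nothing forbids following up a main effect, and many analysts would. At the plan's own benchmark, f = 0.54, a main-effect-only result almost never arises if there is no effect at 0 mg cocaine.

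Much of this stands, and it rules out several stronger readings that a reader might infer.

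- *The plan cannot tell attenuation from augmentation.* Not supported: the means show it descriptively. What is missing is a planned test, and reading the means is unreliable only for mixed patterns.
- *The ANOVA or the design is invalid.* Not supported: the omnibus tests are unaffected.
- *All outcomes share the gap.* Not supported: peak and AUC analyses carry the same gate, but the time-course analyses of those data have ungated comparisons.
- *The gap will usually bite at the effect the plan expects.* Not supported for break points under step 3. However, the benchmark comes from another drug, and smaller effects are possible.

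What the reply does not remove: a follow-up improvised after the data are seen would leave family, error term and required direction to be chosen then. It also does not cover an effect that is equal across cocaine doses.

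**Conclusion.** The point holds as a gap in the decision rule for break points and impulsivity. A main-effect-only result would be declared an augmentation or attenuation of cocaine's effects with no dose tested against placebo, with direction read only from the means, and without evidence that the cocaine dose-response curve has shifted.

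Its size depends on assumptions that the documents do not fix. At the smallest detectable effect it touches about 46% of trials with equal SDs and 25% with SDs 4:15:22. At the plan's benchmark it touches under 1% and 0%. For an effect equal at all cocaine doses with equal SDs it touches 88% to 95%, whatever the effect size. Separately, the either-or rule declares an effect in about 9% to 11% of trials with no true effect. The plan should be changed, but the gap does not undermine the trial.

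**What to change.** For break points and impulsivity outcomes, add to Section 7:

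1. If the zolmitriptan main effect is significant and the interaction is not, compare each active dose with placebo on the means averaged over cocaine dose. Use Tukey on four means with the zolmitriptan-by-subject error (57 df, critical difference 2.65 SE), or three Holm-adjusted contrasts. Report sign and estimate.
2. Conclude an effect only when such a comparison, or a post-interaction comparison at an active cocaine dose, is significant, and take the direction from its sign. State the attenuation sign for every outcome: cocaine break point down, money break point up, discounting rate k down, n-back percent correct up, stop-signal inhibitory failures and inhibition latency down.
3. After a main-effect-only result, word the conclusion as a change averaged over cocaine dose and report the 0 mg cocaine comparison. Do not call it attenuation of cocaine's effect if the 0 mg condition shifts equally.
4. Name the Tukey family used after an interaction, for example four zolmitriptan means within each cocaine dose (2.61 SE) or all 12 means (3.34 SE).

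The same wording could be applied to the peak and AUC analyses for consistency.

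**Cost.** A few lines of text and SPSS syntax, with no change to design or data. Fewer effects will be declared. With equal SDs and the four-mean family, declarations fall from 95% to 93% at D = 0.72, from 84.5% to 78.4% at D = 0.6, and from 66% to 59% for 0.72 at 30 mg only. With the 12-mean family they fall from 95.2% to 87.3% at D = 0.72 and from 84% to 70% at D = 0.6. Averaging over cocaine dose dilutes an effect confined to one dose.

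**Gain with no true effect.** Declarations fall from 9.4% to 4.1% with equal SDs and the four-mean family. With SDs 4:15:22 they fall from 10.9% only to about 7%; the 12-mean family brings them to about 5%. The choice of family is therefore a trade-off to settle before unblinding.
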